## 13.4.4 Analyses of Secondary Endpoints

All secondary inferential analyses are considered supportive; p-values for test of differences among groups will be presented without adjustment for multiple comparisons. The mITT population will be used for all secondary analyses. For secondary response indices (e.g. F-VASI25 at Week 12, F-VASI25 at Week 36, F-VASI25 at Week 48, T-VASI25 at Week 12, etc.), participants for whom endpoint data is unavailable will be deemed response failures. Otherwise, data will not be imputed for analyses of secondary endpoints.

The null hypothesis proposes that there are no differences in the secondary endpoints (measured either as means or proportions) between study groups. The alternative hypothesis proposes that there are differences between groups.

The following analyses are planned to evaluate the impact of treatment over the course of the study:

- 1. For secondary dichotomous response variables including F-VASI25, F-VASI35, F-VASI35, F-VASI50, F-VASI75, F-VASI90, T-VASI25, T-VASI35, T-VASI50, T-VASI75, and T-VASI90 at each indicated secondary analysis time point, analyses will be analogous to those described for the primary endpoint.
- 2. Estimated response rates for each dichotomous F-VASI and T-VASI responder variable (i.e. 25%, 35%, 50%, 75%, 90%) at each indicated analysis time point will be presented for subgroups defined by treatment and active/stable vitiligo status.
- 3. For the change (and % change) in F-VASI, change (and % change) in T-VASI, change in VES, and change in VitiQoL at each indicated secondary analysis time point, the treatment group distributions will be compared using Mann-Whitney tests (2-sided).
- 4. For the ordinal VNS endpoint at each secondary analysis time point,
  - a. Treatment groups will be compared at each indicated secondary analysis time point using an extension of the Fisher's Exact test.
  - b. Shifts in distributions from baseline to each time point will be evaluated for each treatment arm using Bowker's exact test of symmetry.

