5. To evaluate treatment group differences longitudinally, separate general mixed linear models will be fit to the F-VASI, T-VASI, VES, and VitiQoL, over all time points from day 0 through Week 24 with fixed effects for time point (fit as categorical), treatment group and the time\*treatment interaction. A 1-banded unstructured within-subject covariance matrix will be assumed and fit separately for each treatment arm. Appropriate contrasts will evaluate trends over time and changes from baseline.

After Week 24, participants who do not achieve a T-VASI25 response will receive nbUVB phototherapy. For T-VASI25 responders (who will not receive nbUVB phototherapy), the post-Week 24 analyses will evaluate durability of response. In contrast, for T-VASI25 non-responders, the aim will be to evaluate improvement following the addition of nbUVB phototherapy. The following analyses are planned:

- 1. Durability of response: For the subset of participants who achieve a T-VASI25 response at Week 24 (and receive no nbUVB phototherapy), the null hypothesis of no change from Week 24 to Week 48 will be evaluated by treatment arm against the 1-sided alternative of worsening from Week 24 to Week 48.
  - a. For each treatment arm, descriptive statistics and p-values derived from Wilcoxon tests will be presented for change (and % change) in F-VASI, change (and % change) in T-VASI, change in VES, and change in VitiQoL from Week 24 to Week 48.
  - b. For the VNS ordinal endpoint, shifts in distributions from Week 24 to Week 48 will be evaluated for each treatment arm using Bowker's exact test of symmetry.
- 2. Improvement after nbUVB phototherapy: For the subset of participants who do not achieve a T-VASI25 response at Week 24 and receive nbUVB phototherapy, analyses will assess improvement in repigmentation and other key scales in the AMG 714 and placebo arms following nbUVB phototherapy.
  - a. For each treatment arm, descriptive statistics and p-values derived from Wilcoxon tests will be presented for change (and % change) in F-VASI, change (and % change) in T-VASI, change in VES, and change in VitiQoL from baseline to Week 48.
  - b. For dichotomous response indices defined by % improvement from baseline to Week 48 (i.e. F-VASI25, F-VASI35, F-VASI50, F-VASI75, F-VASI90, T-VASI25, T-VASI35, T-VASI50, T-VASI75, and T-VASI90), estimated response rates will be presented for subgroups defined by treatment.
  - c. For the VNS ordinal endpoint at Week 48,

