Hepatitis C (RNA or antibody)	X													
Quantiferon-TB Gold/Quantiferon-TB Gold Plus 	X													
Serum pregnancy	X													
STAT urine pregnancy		X	X	X	X	X	X	X		X	X	X	X	
	V	ITIL	IGO A	ASSE	SSMI	ENTS					I	l	l	
F-VASI	X	X			X			X		X	X	X	X	X
T-VASI	X	X			X			X		X	X	X	X	X
VES		X			X			X		X	X	X	X	
VitiQoL		X			X			X		X	X	X	X	
VNS					X			X		X	X	X	X	
sIGA		X						X		X	X	X	X	
Digital skin photography		X						X		X		X	X	

<sup>8 PPD skin test may be substituted.

Phase of Trial	SCRN			Dos	sing				Post-t	reatme	ent (FU	) 	WD 	UN 
Week		0	2	4	6	8	10	12	18	24	36	48	WD	U
Visit 	V-1	V0	V1	V2	V3	V4	V5	V6	V7 	V8	V9	V10	WD	U
	MECHANISTIC ASSESSMENTS													
Skin biopsy – lesional 		X						X		X		X	X	
Skin biopsy – non-lesional		X						X						
PBMCs		X			X			X		X	X	X	X	
Serum		X			X			X		X	X	X	X	
Whole blood RNA		X			X			X		X	X	X	X	
Whole blood DNA		X			X			X		X	X	X	X	

Protocol ITN086AI: REVEAL

Version 4.0

November 3, 2023

 $^{9}$  If the lesion has resolved, the punch biopsy will be taken from the previously lesional area.

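### The banded covariance in the longitudinal models sets the Week 0–Week 12 and Week 0–Week 24 covariances to zero, so the standard errors for those changes from baseline are too large

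*Combined protocol and SAP*

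**What the plan says.** Section 13.4.4, item 5, plans a longitudinal comparison with one mixed model for each of four scores: F-VASI, T-VASI, VES and VitiQoL. Each model runs "over all time points from day 0 through Week 24 with fixed effects for time point (fit as categorical), treatment group"; a time-by-treatment interaction is the only other term listed. Week 0 is therefore part of the response vector, not a covariate. The only sentence on dependence within a participant is "A 1-banded unstructured within-subject covariance matrix will be assumed and fit separately for each treatment arm". The use of the model follows directly: "Appropriate contrasts will evaluate trends over time and changes from baseline".

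The Schedule of Events (Appendix 1) places all four scores at Weeks 0, 6, 12 and 24 within this period. No random subject effect, robust (sandwich) standard error or fallback structure is stated.

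On status, the same section says "All secondary inferential analyses are considered supportive". Item 3 separately tests the changes in these four scores with two-sided Mann-Whitney tests at the secondary time points.

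**The concern.** The variance of a change from baseline contains minus twice the covariance between baseline and the later visit. With only fixed effects in the model, that covariance can come only from the stated matrix. Counting scheduled visits, Week 12 is two steps from Week 0 and Week 24 is three. A single band reaches one step at most, so the term is dropped for exactly the changes of interest.

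With complete data the point estimates do not move, but the confidence intervals are too wide and the p-values too large. In a proof-of-concept trial of 57 people, the longitudinal model could miss an effect on mean change that the Mann-Whitney test on the same change finds, and the cause would be the covariance restriction. On the diagonal reading the model also takes no information from earlier visits when a later one is missing. That would remove a main reason for having it, since continuous secondary endpoints are not imputed.

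**Working it through.** **Inputs.** Visits at Weeks 0, 6, 12 and 24 (Appendix 1). Fixed effects and banded matrix (13.4.4, item 5). Sample size 57 at 2:1, so 38 and 19 (13.7). The documents give no SD or correlation and no standard error for these models, so there is no stated figure to reproduce. Assumptions: equal SDs, and a correlation ρ between baseline and later visit from 0.3 to 0.9, either constant or decaying. Positive correlation is the natural expectation. Baseline F-VASI can run from 0.25 (inclusion criterion) to 3.5 (facial maximum, Appendix 2), and only 5% of placebo participants are assumed to improve by 35% (13.7).

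**Two readings of the band.**
- Diagonal only: all covariances are zero (4 parameters per arm).
- Diagonal plus one off-diagonal: Weeks 0–6, 6–12 and 12–24 covary; Weeks 0–12, 0–24 and 6–24 do not (7 parameters per arm).

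The Week 0–12 and Week 0–24 covariances are zero on both. The Week 0–6 covariance is lost only on the first.

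**Standard error.** In SD units, Var(change) = 2(1 − ρ) per participant; with the covariance set to zero it is 2. The ratio of model SE to true SE is 1/√(1 − ρ).

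For the between-arm difference in change, the true SE is √[2(1 − ρ)(1/38 + 1/19)]. With the covariance at zero it is √[2(1/38 + 1/19)] = 0.397 SD at every ρ, against true values of 0.281 (ρ = 0.5), 0.218 (0.7), 0.178 (0.8) and 0.126 (0.9).

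For the one-band reading, the tridiagonal matrix closest to the true one in Gaussian likelihood was found numerically. SE ratios under constant correlation:

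| ρ | Diagonal, every visit | One band, Week 12 | One band, Week 24 |
|---|---|---|---|
| 0.3 | 1.20 | 1.19 | 1.20 |
| 0.5 | 1.41 | 1.40 | 1.41 |
| 0.7 | 1.83 | 1.80 | 1.83 |
| 0.8 | 2.24 | 2.22 | 2.24 |
| 0.9 | 3.16 | 3.16 | 3.16 |

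The one-band Week 6 ratio is 1.00 to 1.03 under constant correlation.

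**Decaying correlation.**
- Decay per visit, adjacent correlation 0.5, 0.7 or 0.9: the Week 0–24 correlation is the cube (0.125, 0.343, 0.729), and the Week 24 ratio is 1.07, 1.23 or 1.92 on both readings.
- Decay per six weeks at 0.8, 0.9 or 0.95: the Week 24 ratio is 1.30, 1.71 or 2.32 on both readings. The one-band Week 12 ratio is 1.59, 2.19 or 3.17, and its Week 6 ratio lies between 1.02 and 1.23.

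**Power and type I error at Week 24.** Simulation at 38:19 with complete data, per-arm variances and Satterthwaite degrees of freedom. There were 20,000 runs per ρ, except for the one-band fit (300 runs per ρ, so a Monte Carlo SE of √(0.25/300), about 3 points, near 50%). The effect was set so that the full unstructured matrix has about 80% power.

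| ρ | Diagonal | One band | Type I error, diagonal |
|---|---|---|---|
| 0.3 | 69% | 68% | 0.022 |
| 0.5 | 52% | 53% | 0.007 |
| 0.7 | 24% | 25% | 0.0005 |
| 0.8 | 8% | 6% | below 0.0001 |
| 0.9 | 0.2% | 0.3% | below 0.0001 |

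The Mann-Whitney test on change keeps 78–79%.

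**Hand check.** With SE ratio k, normal-theory power is Φ(2.80 − 1.96k), where 2.80 = 1.96 + 0.84 corresponds to 80%. For k = 1.195, 1.414 and 1.826 this gives 68%, 51% and 22%, close to the simulation. Applied to per-visit decay (k = 1.069, 1.234, 1.921), it gives about 76%, 65% and 17%.

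**The case against.** The strongest reply is that the plan calls these mixed models and attaches the band to the within-subject matrix. A random subject effect may have been meant alongside it, and that would restore the covariances. This is possible, but none is written. The sentence needs changing either way.

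Second, the harm is limited. The models are supportive, and every listed change in these four scores at Weeks 12 and 24 also has a Mann-Whitney test that does not use this matrix. That stands and limits the importance of the point. It does not make the stated standard errors right.

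Third, the steepest power losses need constant correlation of 0.7 or more over 24 weeks. Under decay the loss can be small: with an adjacent correlation of 0.5 the Week 24 ratio is only 1.07. That also stands, so the size is a range that depends on an unstated input.

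Fourth, the conservative direction applies only to change contrasts. On the diagonal reading with constant ρ, a treatment contrast averaged over the four visits has SE ratio 1/√(1 + 3ρ), about 0.57 at ρ = 0.7, which is too small. This is correct, and it gives no support to the banded matrix.

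Fifth, the simulation used complete data and Satterthwaite degrees of freedom. It did not test Kenward-Roger, dropout or a fallback sequence with 19 placebo participants. That limits what it shows about the remedy, but not the fault.

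**Conclusion.** The concern holds. As written, the model fixes the Week 0–12 and Week 0–24 covariances at zero on either reading of the band, and the changes from baseline at those visits get standard errors that are too large if within-person correlation is positive. Under constant correlation of 0.3 to 0.9 the Week 24 inflation is 1.20 to 3.16 times; under decay it ran from 1.07 to 2.32 in the cases examined. For these contrasts the cost is lost power, not false positives, and complete-data estimates are unchanged. The conclusion rests on the absence of a random subject effect or robust standard errors, and its size on assumed correlations. The primary analysis and the Mann-Whitney tests are unaffected. It should be fixed, because a stated rule works against the model's stated purpose, but it does not threaten the trial's main conclusion.

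**What to change.** Replace the covariance sentence in 13.4.4, item 5, with wording such as: *A full unstructured 4×4 within-subject covariance (Weeks 0, 6, 12, 24) will be fitted separately for each treatment arm, with Kenward-Roger degrees of freedom. If this does not converge, it will be pooled across arms; then heterogeneous Toeplitz; then heterogeneous AR(1).* Any fallback should keep a non-zero covariance between all pairs of visits. If a random subject effect was intended with the banded matrix, state it instead, and say which meaning of the band applies.

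The cost is one sentence, one line of code and no new data. The downside is 10 covariance parameters per arm instead of 4 or 7, and a possible need for a fallback with 19 placebo participants. With complete data, the per-arm full matrix held type I error at 0.049–0.054 in the simulation (Satterthwaite degrees of freedom). Behaviour with dropout was not examined, so the convergence sequence should be tried on simulated incomplete data before unblinding.

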#### 3.3 SECONDARY ENDPOINTS

## 3.3.1 Secondary Efficacy Endpoints

- 1. Proportion of participants with F-VASI35 at Weeks 12, 36, and 48.
- 2. Proportion of participants with F-VASI25, F-VASI50, F-VASI75, and F-VASI90 at Weeks 12, 24, 36, and 48.
- 3. Proportion of participants with T-VASI25, T-VASI35, T-VASI50, T-VASI75, and T-VASI90 at Weeks 12, 24, 36 and 48.
- 4. Change in each of the following at Weeks 12, 24, 36, and 48 compared to Week 0:
  - a. F-VASI
  - b. T-VASI
  - c. Vitiligo Extent Score (VES)36
  - d. Vitiligo Quality of Life instrument (VitiQoL)
  - e. Vitiligo Noticeability Scale (VNS)38
  - f. Static Investigator Global Assessment (sIGA)
- 5. Percent change in each of the following at Weeks 12, 24, 36, and 48 compared to Week 0:
  - a. F-VASI
  - b. T-VASI

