    - i. Shifts in distributions from baseline to Week 48 will be evaluated for each treatment arm using Bowker's exact test of symmetry.

Treatment group differences for the incidence of AEs and the incidence of grade 3 or higher infectious AEs occurring over the first 24 weeks will be compared using a Fisher's exact test.

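### Improvement after nbUVB is measured only from Week 0, so change before phototherapy can pass for it or hide it; separately, the VNS baseline comparisons have no baseline score

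*Combined protocol and SAP*

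**What the plan says.** Section 13.4.4 splits the post-Week 24 analyses by T-VASI25 status at Week 24. For non-responders, who receive nbUVB, it states that "the aim will be to evaluate improvement following the addition of nbUVB phototherapy". Section 7.3 ties nbUVB to the Week 24 T-VASI result and allows up to 28 days from that visit to start it. Section 8.2.2 defines baseline as Week 0.

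Three analyses are listed for the nbUVB subset:

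- Item 2a, continuous scales: change in F-VASI and T-VASI (absolute and percent), "change in VES, and change in VitiQoL from baseline to Week 48".
- Item 2b, response rates: "For dichotomous response indices defined by % improvement from baseline to Week 48".
- Item 2c, VNS: "Shifts in distributions from baseline to Week 48 will be evaluated for each treatment arm".

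For T-VASI25 responders, by contrast, "the null hypothesis of no change from Week 24 to Week 48 will be evaluated by treatment arm".

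On VNS for the whole trial, Section 13.4.4 item 4b says "Shifts in distributions from baseline to each time point will be evaluated for each treatment arm". Section 3.3.1 endpoint 4, which includes VNS as 4e, is "Change in each of the following at Weeks 12, 24, 36, and 48 compared to Week 0"; the synopsis lists the same endpoint. The Schedule of Events (Appendix 1) has VNS at Weeks 6, 12, 24, 36, 48 and withdrawal, with no mark at screening or Week 0. The VNS question in Appendix 5 asks the participant to compare the present with the time before treatment.

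**The concern.** A result reported as improvement after phototherapy will be read as what happened once phototherapy began. The first half of the Week 0 to Week 48 interval lies before nbUVB and contains all six study-drug doses. A gain made in that half is carried into the result, and a loss made in that half is subtracted from it. A reader of the Week 48 tables could then credit nbUVB with repigmentation already present at Week 24, or miss a real recovery after Week 24.

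The VNS fault is of another kind. Bowker's test needs a score from each participant at both times, and the plan collects no score at the first.

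**Working it through.** **No figure to reproduce.** The plan gives no number for these analyses. The power figures in Section 13.7 concern the Week 24 primary comparison and use no Week 48 data.

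**Step 1. Does any planned analysis of the nbUVB subset cover Weeks 24 to 48?** From Section 13.4.4:

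| Analysis | Participants | Interval |
|---|---|---|
| Items 1 to 3: response rates, change scores | all mITT | Week 0 to each visit |
| Item 5: mixed models | all mITT | "over all time points from day 0 through Week 24" |
| Durability, item 1 | T-VASI25 responders | Week 24 to Week 48 |
| After nbUVB, items 2a to 2c | non-responders given nbUVB | Week 0 to Week 48 |

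None does. The interval that fits the stated aim is used only for the participants who do not receive nbUVB.

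**Step 2. Effect on T-VASI change (item 2a).** Improvement from Week 0 = (W0 − W48)/W0; improvement from Week 24 = (W24 − W48)/W24. The values are illustrative.

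| T-VASI at Weeks 0 / 24 / 48 | From Week 0 | From Week 24 |
|---|---|---|
| 10 / 8 / 8 | 2/10 = 20% | 0/8 = 0% |
| 10 / 12 / 10 | 0/10 = 0% | 2/12 = 16.7% |
| 10 / 7.6 / 7.4 | 2.6/10 = 26% | 0.2/7.6 = 2.6% |

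All three participants are below 25% improvement at Week 24 (20%, −20% and 24%), so all belong to the subset. Earlier T-VASI gain is therefore limited to just under 25% of Week 0. Earlier worsening has no corresponding limit.

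**Step 3. Effect on T-VASI thresholds (item 2b).** Nobody in the subset has reached T-VASI25 or higher at Week 24, so any crossing occurs later. Earlier gain can still supply most of it: in the third row, 24 of the 26 percentage points were present before nbUVB, and the participant becomes a T-VASI25 responder at Week 48.

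**Step 4. Effect on F-VASI thresholds (item 2b).** Subset entry depends on T-VASI alone, so an F-VASI threshold may already be met at Week 24. Take Week 0 values equal to the entry minimums in Section 4.2 (F-VASI 0.25, T-VASI 3), and take the facial part of T-VASI as equal to F-VASI. Full facial clearing with no change elsewhere then lowers T-VASI by 0.25/3 = 8.3%. This participant meets F-VASI90 at Week 24, enters the subset, and if unchanged is an F-VASI90 response at Week 48 under the nbUVB heading.

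The same can happen with a success on the primary endpoint. A 35% facial improvement with no change elsewhere gives a T-VASI25 response only if the face makes up at least 0.25/0.35 = 71% of T-VASI.

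**Step 5. VNS.** Bowker's test compares paired scores on one scale. Items 4b and 2c name baseline as the first member of the pair, and no such score is scheduled. Nor would adding a Week 0 visit supply a meaningful one, because the question already asks about change since before treatment. Endpoint 4e fails for the same reason. The Week 24 to Week 48 VNS shift in durability item 1b, and the between-arm comparison at each visit in item 4a, can both be run on the scores as collected.

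**The case against.** The best defence is that Week 0 is the plan's consistent reference. Objective 4 in Section 2.3 concerns AMG 714 followed by nbUVB, Section 3.1 describes change through Week 48 with or without nbUVB, and every change endpoint in Section 3.3.1 is against Week 0. On that view a Week 0 to Week 48 improvement is a true statement about the whole sequence and misleads only through its label. This stands in part: a reader might infer that the Week 0 to Week 48 analysis is invalid and should go, and the documents do not support that. It answers objective 4. It does not answer the aim that Section 13.4.4 sets for this subset.

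A second objection is that Week 24 to Week 48 change would not establish an nbUVB effect either. That stands in full. The subset is selected on a poor Week 24 T-VASI, so some later improvement is expected from regression to the mean. Classifying participants by Week 24 F-VASI status adds the same problem. There is no non-responder group without nbUVB, and up to 28 days may pass before nbUVB starts. These limits restrict what may be claimed from the added analysis; they are not a reason to omit it.

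Third, the facial-clearing example is an extreme, and the likely size of carry-over cannot be known. That is fair. The documents give no distribution of Week 0 to Week 24 change, no measurement error, and no overlap between F-VASI and T-VASI response. A reader might want a false-positive rate for item 2a; any such figure would rest on invented inputs, so none is given.

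**Conclusion.** Both faults hold on the text. First, the analyses of improvement after nbUVB do not isolate the period after nbUVB, and nothing else in the plan does so for these participants. The T-VASI carry-over limit and the possibility of F-VASI thresholds being met before phototherapy follow from the subset definition. The worked values are illustrative, and the 8.3% and 71% figures also assume that the facial part of T-VASI equals F-VASI. How often this would occur cannot be determined from the documents.

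Second, and independently, the baseline VNS shift tests and the VNS change-from-Week-0 endpoint cannot be computed as written. This needs no assumption.

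The consequence is moderate. Section 13.4.4 calls the secondary analyses supportive and leaves them unadjusted, and item 2 contains no between-arm test. A reader might infer that the trial's main result is at risk; it is not, because the primary analysis, sample size and power use none of these comparisons. The point should be fixed because the wrong interval bears directly on what is concluded about phototherapy, and the correction needs no new data.

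**What to change.** In Section 13.4.4, post-Week 24 item 2:

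- **2a.** Add within-arm change from Week 24 to Week 48 in F-VASI, T-VASI, VES and VitiQoL as the analysis of improvement after nbUVB. Use absolute change for F-VASI, with percent change descriptive only, because Week 24 F-VASI can be near zero in this subset.
- **2b.** For each F-VASI threshold, cross-tabulate Week 24 against Week 48 status by arm, showing both those who newly reach it and those who lose it. Counting only new responders would be one-sided. Keep the T-VASI thresholds, with a note that they include change before Week 24.
- **2c.** Replace the baseline VNS shift with the Week 24 to Week 48 shift.

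Elsewhere:

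- Drop the baseline VNS shift test in item 4b. In endpoint 4e (Section 3.3.1 and synopsis), define VNS as the score at each visit, with the share scoring 4 or 5, the success criterion in Appendix 5.
- Keep the Week 0 to Week 48 results for the VASI scales, VES and VitiQoL, relabelled as total change over study drug followed by nbUVB, for objective 4.
- State the limits beside the new analyses: regression to the mean from selecting on Week 24 T-VASI and from conditioning on Week 24 F-VASI status, no untreated non-responder group, and up to 28 days before nbUVB starts. The Week 24 to Week 48 change describes that period and does not prove an nbUVB effect.

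The cost is wording in the protocol and analysis plan and a few table rows. Appendix 1 already schedules all five scales at Weeks 24 and 48.
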